Overview: The study is a randomized controlled trial (RCT) that will compare computerized EF training administered prior to CPT (CEFT-CPT) to a placebo word game training prior to CPT (WT-CPT). Goals of the research include 1) examining whether CEFT improves EF in OEF/OIF Veterans with PTSD and whether this in turn mediates PTSD symptom improvements, 2) investigating the efficacy of CEFT-CPT in improving treatment adherence, completion rates, and psychological and functional outcomes, and 3) determining whether baseline measures of EF predict treatment response. Veterans will be enrolled from the VASDHS system of PTSD clinics, spanning the main and 3 satellite facilities, and general outpatient mental health clinics. Assessments will be administered at baseline, immediately after CEFT or word training (prior to CPT), and after CPT completion.

Participants:

Inclusion criteria: 1) OEF/OIF Veterans enrolled at VASDHS, 2) aged 18-55 3) current PTSD diagnosis, 4) endorsement of cognitive complaints, 5) no pending medication changes, 6) English-speaking. Given the potential impact on outcome variables of interest, we will track current medication use in enrolled Veterans to ensure no recent or pending changes.

Exclusion criteria: 1) active substance use disorder in the last month, 2) suicidal intent or attempt within the last month, 3) schizophrenia, psychotic disorder and/or bipolar disorder, 4) dementia, 5) premorbid IQ < 70, 6) participation in other concurrent PTSD intervention studies, 7) previous completion of more than 4 CPT sessions, 8) history of a documented neurological disorder (e.g., Parkinson's disease, multiple sclerosis, epilepsy) 9) moderate to severe TBI (loss of consciousness greater than 30 minutes or post-traumatic amnesia greater than 24 hours).

Further exclusion criteria details: A history of mild TBI is highly comorbid in OEF/OIF but the majority of the literature supports a mental health etiology to persistent symptoms following mTBI; the current study will account statistically for mTBI history but it is not exclusionary.

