During recruitment, we will initially screen Veterans by phone. Those that are eligible for the study based on the phone screen will be brought to the lab for consenting, intake, and baseline assessments (approximately 200 Veterans). However, we assume a portion of those individuals will not qualify for the study. That will leave us with approximately 150 Veterans (75 per condition) to randomize to treatment. For recruitment, we will utilize the VASDHS system of PTSD clinics, spanning the main and 3 satellite facilities, and general outpatient mental health clinics. VA employees are not the target population, however they will not be excluded if they meet the inclusion criteria.

Financial Incentives: Participants will be compensated for their time after each completed assessment. Veterans will receive \$50 for the baseline assessment (\$30 for completion of the questionnaires and

neuropsychological assessment, \$20 for the fMRI assessment), \$30 as a bonus for completing at least 80% of the cognitive training (or placebo word games), \$50 for the post-computerized training assessment, and \$70 for the post-therapy assessment (Total possible = \$200).

Procedures:

Design and methods: Veterans will be randomized to either 12 weeks of CEFT-CPT or placebo word training plus CPT. Assessments will be administered three times: at baseline, immediately after CEFT or word training (prior to CPT), and after CPT completion. Assessment of PTSD diagnosis, symptom severity, quality of life, and subjective and objective measures of cognition will be administered at baseline (prior to computerized training onset), immediately after completing the cognitive training portion of the study (i.e., 6 weeks after baseline, just prior to starting CPT), and after completion of CPT treatment (approximately 6 weeks later, a total of 12 weeks after study initiation). Treatment satisfaction will be assessed after CEFT and CPT completion. Symptom severity will also be assessed at the midway point for the cognitive training and weekly during the CPT intervention component. Functional neuroimaging during rest and during two well-validated EF tasks will be collected at baseline, a Go-No Go Task that taps inhibition and an N-Back Task that taps working memory.

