Acquisition of images: All scans will be collected on a research-dedicated 3T General Electric (GE) Discovery MR750 whole body system using a 32-channel receiver coil (Nova Medical Inc, Wilmington MA). An initial localizer scan will be acquired to assure proper positioning in the scanner and to allow for slice prescription. An anatomical scan will be collected for registration of functional data to standard space. Blood oxygenation level dependent (BOLD) signal will be measured using gradient echo planar imaging during the functional tasks. In addition, two field maps will be collected to assist with distortion correction of the BOLD images.

Resting state: Resting state data will be acquired for 8 minutes via T2-weighted functional images using a gradient-echo multiband echoplanar imaging method. Participants will be instructed to remain still, stay awake, keep their eyes open, and focus on a fixation point.

Computerized EF Training: CEFT will consist of 6 weeks of online training 30 minutes a day for 5 days a week on a home computer followed by the standard protocol of the cognitive-only version of CPT (CPT-C) for 6 weeks (2 sessions per week). CEFT will be administered via BrainHQ by Posit Science and will consist of six cognitive training modules that target executive processes of inhibition, shifting, and updating of working memory. All tasks become more challenging with practice. Veterans will receive a brief introduction to the program on site at the VA (log-in, which modules to complete, and how long to spend each day on the training). These instructions will be provided in a written format to be used once participants are on their home computer. If participants do not have a home computer/internet access, they can complete the modules at another location such as a public library or at the VA, but training will still be self-directed. BrainHQ offers a secure portal that allows for monitoring of usage and progress of participants. Researchers will be in weekly phone contact with participants to check on their progress with the cognitive training and answer any questions. This check-in will also serve the purpose of keeping them engaged and motivated.

BrainHQ Modules:

1. Mind Bender: cognitive flexibility/set shifting exercise, participants switch between two different rules in order to make correct responses

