The exclusion criteria involving specific DSM-5 (Diagnostic and Statistical Manual-5) disorders, including substance use disorder, schizophrenia, psychotic disorder, bipolar disorder, and dementia (criteria 1, 3, 4) will be determined based on a CPRS chart review for clinical assessments that determine diagnosis based on DSM-5 criteria. We will also ask them during the phone screen about diagnoses. If there is any ambiguity in terms of psychiatric diagnoses based on the phone screen and a review of patient records (CPRS) that would disqualify the participant, the relevant portions of the MINI International Neuropsychiatric Interview (MINI; Sheehan, 2014) will be administered during the baseline assessment to clarify eligibility, as noted in the methods section. CPRS will also be reviewed for evidence of suicide intent or attempt within the last month (criteria 2), including a review of their Comprehensive Suicide Risk Assessment (CSRA) documented in CPRS. We will also ask them during the baseline assessment, including during the completion of the Beck Depression Inventory-II (BDI-II) that has a question about suicidal intent. An endorsement of a 1 or higher on this item will prompt further assessment for intent as described in the suicidality form. Premorbid IQ below our cutoff (criteria 5) will be determined either by a chart review if the participant received a previous clinical neuropsychological assessment documented in CPRS or by administering the WRAT5 during the baseline assessment (see methods section). Criteria 6, 7, 8, 9 will be determined by a CPRS chart review and also based on participant answers to the relevant questions on the phone screen. If the severity of any TBIs experienced (criteria 9) is ambiguous, eligibility will be determined by the Ohio State University TBI Interview administered at the baseline assessment (see methods section).

Veterans will not be excluded for current psychotropic medication usage or past mental health treatment that was not CPT, but given the potential impact on outcome variables of interest, we will track duration and type of past mental health therapies as well as current medication use in enrolled Veterans.

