Other potential MR risks. The subject will be informed during the consent process that the scans are not optimal for diagnosing a brain disorder. Yet some abnormalities might be observed on the scans. Should there be cause for concern, with permission of the participant, any clinically important observations will be forwarded to his/her primary care physician for follow-up. Although it is possible to reconstruct a form of the facial features from the MRI data, the likelihood that this information could be used to identify a person with the reliability of a photograph has not been confirmed by research to date, making these reconstructions not comparable to photographic images. It is preferable to maintain the facial features in the MR images for purposes of later data analysis and skull reconstruction. As part of the authorization and informed consent process, subjects will be informed of the slight risk of potential identification based on reconstruction of MR images and will give authorization to disclose this information to study investigators.

The process of being asked about the presence of a mental health diagnosis during the telephone screen may cause temporary discomfort and Veterans can be reminded of immediately accessible clinical services available to them (e.g., VA Psychiatric Emergency Clinic) in the event of any significant discomfort.

Risk of emotional discomfort that can arise during Cognitive Processing Therapy will be addressed in that all Veterans will see their study therapist biweekly to weekly for the therapy component of the study. [name] will review the assessment and progress of each subject and consult with [name] during weekly meetings. The clinical experience and skill level of personnel will enable study staff to implement protocol procedures with a minimum of psychological discomfort for study participants. All patients will be monitored on a weekly basis, and study personnel will be available during regular business hours to respond to patients' concerns and participants will have emergency contact information for after-hours concerns.

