There is always a risk associated with the management of patients with mood and anxiety disorders that they will develop suicidality. This risk will be carefully mitigated by the systematic and careful assessment of suicidality and homicidality throughout the protocol via weekly in-session assessments made by the therapists. Subjects who develop suicidality will be evaluated by therapist, [name], and [name] to determine whether continued participation in the study is safe and clinically warranted. If the study personnel and participant feel that discontinuation would best suit the participant, the participant will be discontinued from the study, and the participant will be reviewed for appropriate treatment. All mental health staff are trained in and required by the VA to regularly assess suicidality and/or homicidality. If a patient endorses suicidal ideation or homicidal ideation, standard safety procedures are implemented via a licensed psychologist. These depend on the level of threat presented by the patient and may range from making a safety plan with the patient to implementing 5150 procedure for an inpatient hold. Homicidal ideation additionally involves assessment of whether to invoke the Tarasoff law.

For participants who wish to terminate prematurely, we will request a final meeting to assess clinical status and safety and to review reasons for withdrawal (if the participant is willing to share them). Referrals for alternative mental health services, including those in our clinics outside this protocol, will also be provided. Participants enrolled in the study may withdraw at any time without penalty or loss of any benefits or treatment options available to them. Investigators may also withdraw a participant from the study for treatment non-compliance or a newly developed psychiatric or medical problem if, in the opinion of the investigators, these factors interfere with the participant's ability to participate fully in the study. If a participant discontinues the study for any reason, he/she will be offered and allowed access to any care in our clinics that any other patient not associated with the study would receive.

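### Section 15's weekly in-session suicidality check cannot operate in weeks 1-6, when no therapy is scheduled, and no other stated contact is said to ask about suicidality before week 6

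*Combined protocol and SAP*

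**What the plan says.** Section 15 (Risk Management) treats suicidality as a standing risk: "There is always a risk associated with the management of patients with mood and anxiety disorders that they will develop suicidality". The mitigation it offers is "systematic and careful assessment of suicidality and homicidality throughout the protocol via weekly in-session assessments made by the therapists".

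Section 9 (Design and methods; Computerized EF Training; Placebo word games) puts six weeks of computer training or games first in both arms, then six weeks of CPT at two sessions a week. The second full assessment falls "immediately after completing the cognitive training portion of the study (i.e., 6 weeks after baseline, just prior to starting CPT".

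The contacts described for the training weeks are:

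- Weekly calls (Section 9, Computerized EF Training): "Researchers will be in weekly phone contact with participants to check on their progress with the cognitive training and answer any questions". The calls are also meant to keep participants engaged.
- A mid-training measure (Section 9, Design and methods): "Symptom severity will also be assessed at the midway point for the cognitive training and weekly during the CPT intervention component". No instrument is named for the midpoint.
- A general sentence in Section 15, in the paragraph on discomfort during CPT: "All patients will be monitored on a weekly basis, and study personnel will be available during regular business hours". It does not say what is asked.

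At baseline, Section 10 describes chart review, direct questions and the BDI-II item, with this rule: "An endorsement of a 1 or higher on this item will prompt further assessment for intent as described in the suicidality form". The full questionnaire battery, which includes the BDI-II, is repeated after training and after CPT (Section 9, Post-Intervention Assessments). Entry excludes "suicidal intent or attempt within the last month".

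**The concern.** The only ongoing suicidality check with a stated schedule is tied to therapy sessions, and in weeks 1-6 there are none. An ethics committee reading Section 15 would take it that someone asks about suicidality every week of the study. On the stated schedule that holds only for the second half.

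This matters because the protocol itself says the risk is always there, and because the exclusion is narrow. A Veteran with ideation but no recent intent, or with an attempt more than a month ago, can be randomized and then spend six weeks on self-directed training before meeting a study therapist. The Section 15 form prompt also asks, where applicable, what safety information is collected and how often. For suicidality in the training phase, the text gives no frequency.

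**Working it through.** This is a check of a stated safeguard against the stated schedule. It uses no alpha, power or sample-size formula.

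**1. Reproduce the plan's timeline (Section 9).**
- Training 6 weeks + CPT 6 weeks = 12 weeks, as stated.
- 6 weeks × 2 sessions per week = 12 sessions, matching the 12 visits stated under Cognitive Processing Therapy.

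**2. Lay the in-session check over that timeline.**
- Weeks with scheduled therapy sessions: 7-12, so 6 of 12 (50%).
- Weeks without: 1-6, so 6 of 12 (50%), the same in both arms.
- With the planned 150 randomized Veterans (Sections 9 and 10): 150 × 6 = 900 of 150 × 12 = 1,800 Veteran-weeks.

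**3. List every stated contact from baseline to week 6.**

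| Contact | Where | Suicidality question stated? |
|---|---|---|
| Baseline chart review, questions, BDI-II item | Section 10 | Yes |
| Weekly researcher call | Section 9, Computerized EF Training | No: progress, questions, motivation |
| Mid-training symptom severity | Section 9, Design and methods | No: instrument not named |
| Weekly monitoring | Section 15 | No: content not given |
| Week-6 battery | Section 9, Post-Intervention Assessments | Yes, through the BDI-II |

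The interval between stated scheduled suicidality questions is therefore about 6 weeks, against the weekly interval that Section 15 implies.

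**4. Check the narrower reading of Section 15.** Could the word 'protocol' there mean only the CPT protocol? The preceding paragraph speaks of the therapy component when it means CPT. The same part of Section 15 refers to clinics outside this protocol, which points to the whole study. If the narrow reading were right, the sentence would make no promise for weeks 1-6, and Section 15 would then state no scheduled check for training at all. Either way the text needs completing.

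**5. Check the action rule.** The BDI-II rule in Section 10 is written for baseline eligibility. Separately, Section 15 says that endorsed ideation leads to standard safety procedures through a licensed psychologist, without limiting this to a phase. A positive BDI-II item at week 6 or after CPT would therefore probably be acted on. Extending the Section 10 rule makes that explicit.

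**6. Cost the fix.** The calls are described under the active training. The placebo paragraph says that condition controls for contact with research staff, so I assume both arms are called. Calls: 150 × 6 = 900. At an assumed 1-3 extra minutes each: 900 × 1 ÷ 60 = 15 hours, to 900 × 3 ÷ 60 = 45 hours.

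**The case against.** The strongest reply is that missing text does not prove missing practice. Staff speak to participants weekly. The midpoint assessment names no instrument, and the BDI-II is listed among the symptom measures, so it is not ruled out there, although the PCL-5 is the instrument described for regular use. Section 15 says VA mental health staff are required to assess suicidality regularly, Section 14 provides round-the-clock crisis cover, and Section 11 lets usual care continue. Section 10 cites a suicidality form, and the Section 9.9 prompt allows an attached safety plan; neither was available, nor was any call script. In addition, the documents locate added distress in trauma discussion and therapy, not in computer exercises.

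Most of this stands, and it limits the claim. A reader might infer that a Veteran who becomes suicidal during training would be found only by volunteering it or at week 6. The documents do not support that: any of these routes might pick it up. Nor do they suggest that training raises suicidality.

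The reply does not rescue the Section 15 sentence. None of these contacts is said to include a suicidality question, the staff duty has no schedule, the callers are not said to be mental health staff, and crisis cover responds to events rather than looking for them.

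**Conclusion.** The concern holds as a gap between a stated safeguard and the stated schedule. Weekly in-session checks cannot take place in weeks 1-6, which is half of the 12-week study in both arms, and no scheduled suicidality question is stated between baseline and about week 6. This rests only on the protocol's timeline. What remains unknown is whether a form, script or plan outside these documents already covers the training weeks.

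Two further inferences should not be drawn. One is a count of missed episodes: the documents give no event rate, episode length or look-back window, so any such figure would be assumption. The other is that uneven session attendance would bias an adverse-event comparison between arms. The plan contains no such table, and with two CPT sessions planned a week, missing one does not lose the weekly check.

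This is a participant-safety point that should be corrected. It does not affect the efficacy analyses.

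**What to change.** Replace the Section 15 sentence with text along these lines:

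> In weeks 1-6, the weekly staff phone call includes a scripted question on suicidality, worded the same in both arms; a positive answer is passed to a licensed psychologist the same day. During CPT, the therapist assesses suicidality and homicidality weekly in session. The BDI-II rule in Section 10 (a score of 1 or higher prompts assessment of intent) applies at baseline, after training and after CPT.

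If the suicidality form, a call script or an attached plan already sets a training-phase check, citing it in Section 15 is enough. Additional calls in CPT weeks without an attended session, or a new by-arm safety listing, are not needed to cure this defect.

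The cost is a short script, brief training of the callers, and an assumed 15-45 staff hours over 900 calls that are already planned. The downside is some positive answers that need a psychologist's time and turn out to need no action. Endpoints, randomization and sample size are unchanged.

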6) Provide a statement of specific aims and hypotheses that serve as the basis for this protocol. Emphasize those aspects that justify the use of human subjects.

Aim 1: Investigate whether Computerized Executive Function Training (CEFT) leads to objective and subjective improvements in executive functioning and whether this in turn mediates PTSD symptom improvement.

Hypothesis 1a: CEFT will be associated with improvements in both objective and subjective executive functioning.

Hypothesis 1b: Enhanced executive functioning will mediate the relationship between treatment group and PTSD symptom improvement.

Aim 2: Investigate the efficacy of administering CEFT prior to Cognitive Processing Therapy (CEFT-CPT) in improving treatment adherence, completion rates, and outcomes in OEF/OIF Veterans with PTSD.

Hypothesis 2a: Individuals in the CEFT-CPT condition will have greater improvements in PTSD symptoms and quality of life than the control condition (placebo word training plus CPT).

Hypothesis 2b: Individuals in the CEFT-CPT condition will have higher rates of treatment engagement (i.e., completing more hours of homework and attending a greater number of sessions) and higher rates of treatment completion than those in the control condition.

Aim 3: Investigate whether functioning of brain regions in an EF network at baseline predicts treatment response.

Hypothesis 3: Dysfunction in a network of brain regions supporting EF will predict poorer response to treatment. Specifically, those who do not complete treatment and who demonstrate a poorer response will exhibit decreased connectivity between dorsolateral PFC and other regions, including anterior cingulate cortex and parietal cortex, compared to completers and better responders.

Section 7 - Background and Significance

7) Provide a succinct discussion of relevant background information to justify performing the proposed study.

PTSD affects approximately 14% of OEF/OIF Veterans and leads to considerable personal and societal costs (e.g., increased morbidity, reduced work productivity, poorer relationships). Cognitive behavioral therapy (CBT) has been shown to be one of the most effective treatments for PTSD. The Institute of Medicine

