Treatment Randomization: Following baseline assessment, participants will be randomized to the experimental (CEFT-CPT) or control condition (WT-CPT). A computer-generated randomization sequence will be provided by our statistical expert [name] (consultant). Randomization will be stratified by gender to ensure a balanced number of males and females are in each treatment group. Participants, the study assessor, and therapists will be blinded to the experimental treatment condition.

Post-Intervention Assessments (3-4 hours): The full battery of self-report questionnaires measuring psychiatric symptoms, quality of life, and subjective cognitive functioning, objective measures of neuropsychological functioning, and structured clinical interview for PTSD diagnosis will be re-administered twice, once after cognitive training completion and again after CPT completion. For the neuropsychological tests, alternate forms will be used where available and the RCT design will distribute any practice effects equally across the two groups. Participants will also complete the two EF tasks again that were administered at baseline during neuroimaging (though fMRI will not be collected again) or during the baseline assessment if they did not undergo fMRI for safety reasons.

Assessment Measures:

Symptom Measures:

- **PTSD:** The Clinician-Administered PTSD Scale DSM 5 (CAPS-5; Weathers et al., 2013) is the gold-standard, semi-structured interview that corresponds to DSM-5 criteria for PTSD. The CAPS-5 shows strong reliability and validity.

PTSD Checklist for DSM-5 (PCL-5; Weathers, Litz, Keane, Palmieri, Marx, & Schnurr, 2013) will be used to regularly assess PTSD symptomatology at several points throughout the study. The PCL-5 is a 20-item self-report measure of PTSD symptoms with good psychometric properties. The PCL-5 maps directly onto DSM-5 diagnostic criteria.

- **Depression:** Beck Depression Inventory-II (BDI-II; Beck, Steer, & Brown, 1996) is a 21-question multiple-choice self-report inventory, one of the most widely used instruments for measuring depressive symptoms.
- **Subjective day-to-day executive functioning:** Behavior Rating Inventory of Executive Function (BRIEF; Guy et al., 2004) is an ecologically sensitive 75-item self-report questionnaire that measures several aspects of EF in an individual's everyday life in the last month, including inhibition, shifting, working memory, planning/organizing, emotional control, etc.

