Data Analysis: Data management and analysis will be supervised by [name] (Biostatistician and consultant). Data will be analyzed from all randomized subjects on whom we have a baseline assessment and at least one post-baseline evaluation. Every attempt will be made to obtain at least one follow up assessment on any individuals who drop out of treatment. Data will be screened for outliers, missing values, and violation of statistical assumptions. Preliminary analyses will be used to examine the descriptive statistics of the study sample and assess for the influence of outliers and non-normally distributed variables for possible exclusion or transformation. Gender, age, medications, depression, and TBI-related variables will be examined for differences between groups at baseline; they will be added as covariates if differences are significant.

Missing Data: Missing data values will be minimized by intensive training of the staff in techniques of clarifying answers and checking questionnaires while Veterans are on-site. When missing values are identified, several approaches to acquire the necessary data will be employed including 1) contacting the Veterans to obtain the missing data and/or 2) examining the missing data to assess randomness. We expect missing data to be randomly distributed. Missing data (i.e., loss to follow up) will be tested to determine if it is informative, and the methods developed by Diggle (1989) and Ridout (1991) to test for completely random dropouts will be applied. We will test whether the drop-outs are random or systematic by comparing the drop-outs with the study completers on the baseline data. An absence of significant differences would support the random nature of drop-outs. If the extent of missing data is small and the data appear to be consistent with a missing-at-random model (MAR), then the maximum-likelihood analysis using all randomized cases and the observed data is an appropriate method for handling the missing data.

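### Section 15 lets investigators remove a non-compliant Veteran from the whole study, and no text clearly secures that Veteran's post-CPT assessment

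*Combined protocol and SAP*

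**What the plan says.** **The clause.** Section 15 (Risk Management): "Investigators may also withdraw a participant from the study for treatment non-compliance or a newly developed psychiatric or medical problem". The power is optional and conditional. It applies where the investigators judge that the problem interferes with full participation. No level of sessions, homework or training is set.

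**The outcomes it touches.** Hypothesis 2b (Section 6) predicts, for the CEFT arm, "higher rates of treatment engagement (i.e., completing more hours of homework and attending a greater number of sessions) and higher rates of treatment completion". Hypothesis 2a concerns PTSD symptoms and quality of life. The CAPS-5 and WHOQOL-BREF are given at baseline, after training (week 6) and after CPT (about week 12).

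**What the plan does for people who leave.**
- Section 9, Data Analysis: "Every attempt will be made to obtain at least one follow up assessment on any individuals who drop out of treatment".
- Section 9, Missing Data: staff will contact Veterans to obtain values found to be missing. Tests are also planned: methods "to test for completely random dropouts will be applied".
- Section 15: "For participants who wish to terminate prematurely, we will request a final meeting to assess clinical status and safety". This meeting is for Veterans who choose to leave, and no outcome measure is named for it.
- Section 9.9: the number of withdrawals goes to the IRB. Arm, initiator and reason are not requested.

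**Other protections.** Section 9, Treatment Randomization: "Participants, the study assessor, and therapists will be blinded to the experimental treatment condition". The analysis is a mixed model on the full intent-to-treat sample with all available data, and the PCL-5 is collected at mid-training and weekly during CPT.

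**The concern.** Two things are joined that are better kept apart: stopping a treatment and stopping observation. If a Veteran who skips training or CPT sessions is taken out of the study, two consequences follow.

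1. Non-completion in Hypothesis 2b becomes a mixture of Veteran behaviour and staff decisions, with no record that separates them.
2. The week-12 CAPS-5 and WHOQOL-BREF may be lost for Veterans selected for poor engagement. The intent-to-treat analysis needs those values, and the Missing Data text supports maximum likelihood only if missing data are few and consistent with missing at random.

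The existing safeguards leave a gap. A Veteran withdrawn during CPT will normally have had the week-6 visit, so a promise of one or more follow-ups can be read as already kept. A Veteran withdrawn during training could have no post-baseline CAPS-5. Blinding covers therapists, assessor and participants, but the text does not list the investigators or the staff who follow training use ("BrainHQ offers a secure portal that allows for monitoring of usage and progress of participants") and phone Veterans each week.

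**Working it through.** The plan states no withdrawal frequency, SD, correlation or power calculation, so it has no figure of its own to reproduce. Only the 75 per arm, the visit schedule, the visit lengths and the payments below come from the documents. The rest is assumed.

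**Assumed inputs.** CAPS-5 SD 12; correlation 0.6 between visits; compliance 60% (CEFT) and 45% (control); improvement 12 points if compliant and 4 if not, one third of it by week 6. Half of the withdrawals fall in training (weeks 6 and 12 lost) and half in CPT (week 12 lost). Every withdrawn Veteran would otherwise have attended.

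**True difference.** (0.60 − 0.45) × (12 − 4) = 1.20 points.

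**Number affected.** Non-compliers: 0.40 × 75 = 30 (CEFT) and 0.55 × 75 = 41.25 (control), together 71.25. Withdrawing 10% removes 7.1 Veterans; withdrawing 25% removes 17.8.

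**Precision.** With complete data, the standard error of the difference in change is √[2 × 2 × 144 × (1 − 0.6) / 75] = √3.072 = 1.753. With losses, generalised least squares on the three visits gives the values below, with effective n = 75 × (1.753 / SE)².

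| Non-compliers withdrawn (both arms) | SE | Effective n per arm |
|---|---|---|
| 0% | 1.753 | 75 |
| 10% | 1.785 | 72.3 |
| 25% | 1.838 | 68.2 |
| 50% | 1.945 | 60.9 |

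**Bias, Hypothesis 2a.** Large-sample limit of maximum likelihood with arm-by-time means and a common covariance. True value 1.20.

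| Withdrawn (CEFT, control) | Estimated difference |
|---|---|
| 10%, 10% | 1.191 |
| 25%, 25% | 1.163 |
| 50%, 50% | 1.052 |
| 5%, 0% | 1.291 |
| 0%, 5% | 1.105 |
| 25%, 20% | 1.282 |
| 20%, 25% | 1.056 |
| 25%, 0% | 1.694 |
| 0%, 25% | 0.670 |

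Among the 5-point imbalances shown, the largest shift is 1.200 − 1.056 = 0.144 points. That is 0.144 / 12 = 0.012 SD, or 0.144 / 1.753 = 0.08 of a standard error. I varied the correlation (0.4, 0.6, 0.8), the improvements (12/4, 15/4, 12/0, 10/5) and the compliance rates (60/45, 60/60, 50/40, 70/50), which makes 48 sets. Over these, the shift from a 5-point imbalance (25/20, 20/25, 15/10, 10/15) runs from −0.30 to +0.19 points, and the shift from equal 25% use from −0.16 to +0.01. Only one-arm use is large.

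**Simpler cross-check.** Bias = (share of control arm withdrawn − share of CEFT arm withdrawn) × the unrecovered gap in outcome. With 5% of CEFT and 10% of control withdrawn, and a gap of 0.25 to 0.8 SD, this is 0.013 to 0.040 SD.

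**Hypothesis 2b.** The change in the completion gap is k × q / 75, where k is the excess of withdrawals in one arm and q the share of them who would have completed. For k = 5 it is 0, 1.7, 3.3 or 6.7 percentage points for q = 0, 0.25, 0.5 or 1. Among non-compliers q is probably near 0. With equal true completion (30, 38, 45 or 52 of 75), a false p < 0.05 needs 12 would-be completers withdrawn from one arm and none from the other by uncorrected chi-square, or 13 by Fisher or continuity-corrected chi-square: 12/75 = 16% or 13/75 = 17% of that arm.

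**The case against.** The strongest reply is that the plan already covers these Veterans. A Veteran whose non-compliance prompts withdrawal can naturally be called a treatment dropout. The follow-up sentence sets a floor, and does not license skipping week 12. The Missing Data paragraph adds a commitment to contact Veterans for missing values and uses the term to include loss to follow-up. The form also does not use leaving treatment and leaving the study as strict terms. Much of this stands, and it is why the point is small.

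It does not close the gap. The contact commitment sits beside questionnaire checking, so its reach to a whole missed visit for someone already removed is arguable. The authors can draw the distinction when they wish: the Section 15 text on MRI discomfort separates removal from the scanner from removal from the study. The non-compliance clause makes no such separation.

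Three further objections are right. The precision loss is an upper bound, because non-compliers are the Veterans most likely to miss a long visit anyway. The model above uses arm-by-time means, whereas the plan will test random intercepts and slopes. And the discretion is bounded by interference with participation, so it would be wrong to call it unlimited.

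A reader might infer that the clause threatens the validity of Hypothesis 2a, or that it could manufacture a Hypothesis 2b result. The documents do not support either. Therapists and assessor are blinded, which makes one-sided use unlikely during CPT. It is not fully excluded during training, but nothing suggests that it is intended. A reader might also infer that withdrawn Veterans get no follow-up at all; the two Section 9 commitments speak against that.

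**Conclusion.** The point holds as a cheap improvement. The plan permits withdrawal from the study for a behaviour that overlaps its own engagement outcomes, and no sentence clearly secures the post-CPT CAPS-5 and WHOQOL-BREF for those Veterans. Weekly PCL-5 scores soften the loss for symptoms but replace neither measure, and the dropout tests can flag a problem without recovering a visit.

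The likely cost is a little precision: an effective 72 or 68 per arm at worst if 10% or 25% of non-compliers are withdrawn. Bias is negligible under equal use or a modest imbalance. It becomes material only if the clause is used mainly in one arm. All of these sizes rest on assumed inputs, and how often the clause is used cannot be known from the documents.

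**What to change.** 1. **Section 15.** Make treatment non-compliance a ground for stopping study treatment only. Add that the remaining scheduled assessments are still attempted unless consent is withdrawn or assessment is clinically unsafe. Clinical authority to end treatment is unchanged.
2. **Section 9, Data Analysis.** Extend the follow-up sentence to *participants who drop out of treatment or whose treatment is stopped by the investigators, including the post-CPT assessment*. If only one change is made, this one covers most of the problem.
3. **Data capture and reporting.** Record whether the Veteran or the investigators initiated each stop, with date, phase and reason. Count both kinds as non-completers for Hypothesis 2b and report them by arm.

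The Section 14 wording on danger to self or others and the Section 15 wording on suicidality can stay. They concern safety, not non-compliance.

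**Cost.** Wording in two places and a few fields on the stop record. Each retained Veteran needs up to two assessments of 3-4 hours by existing staff and up to $50 + $70 = $120. On the inputs above, half of the Veterans need both visits ($120) and half only the last ($70), an average of 1.5 visits and $95. At 10% use, 7.1 Veterans need about 11 assessments, 32-43 hours and $680. At 25% use, 17.8 Veterans need about 27 assessments, 80-107 hours and $1,690. These totals assume that everyone attends; some will decline.
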